- f. After this baseline testing is complete, subjects will be randomized (using randomization.com to create block randomization) in a blinded fashion to treatment with fenofibrate (160mg/d), a prescription medicine approved by the Food and Drug Administration for treatment of hypertriglyceridemia in adults, or identical-appearing placebo for 12 weeks.
- g. Subjects will be instructed by the study coordinator to continue their usual medications, diet and level of physical activity. They will be given a pedometer to wear daily in order to track their physical activity. Study subjects will be instructed to record blood glucose concentrations and distance walked daily in a study-supplied log. They will also note in this log any side effects, major illnesses or stresses, since TGs are acute phase reactants. Subjects will be asked to either send the log by fax or email to the study coordinator each week or to discuss the log by telephone with the coordinator each week, so that this information can be reviewed by the study investigators.

- h. Through the Lifestyle Intervention Core, subjects will complete a 24-hour dietary recall to provide insight into dietary exposures.

Subjects will return at 6 weeks following start of the intervention for study VISIT 3 for medical monitoring to ensure medical safety. If this visit cannot be scheduled 6 weeks into the intervention due to staffing/scheduling conflicts, it will take place at 5 weeks so that the medical monitoring can be accomplished in a timely fashion.

At this visit:

- a. An interim history will be obtained by the study coordinator and reviewed with the study investigator. Study coordinator will also perform pill counts to assess compliance.
- b. The log of blood glucose, distance walked, side effects and major illnesses/stress will be reviewed by the study coordinator and discussed with the study investigator.
- c. Women will provide a urine sample for a pregnancy test.
- d. Phlebotomy will be performed (6 ml or less than 2 teaspoons) to rule out untoward effects of study drug on kidney or liver function (CMP).
- e. A dietitian will again assist the subject with completing a 24-hour dietary recall.

Subjects will return 12 weeks following start of intervention for study VISIT 4 at CARS for the following:

- a. Urine will be obtained for biochemical analysis of oxidative stress.

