Rare: There is a very slight risk of infection or thrombosis of the vein. Sterile technique will be used in all subjects. Some subjects feel lightheaded during blood drawing. Subjects will be counseled not to donate blood during this study and to be hydrated (adequate oral water intake) before all phlebotomy in order to minimize risks.

Stress Echocardiography:

Likely: Shortness of breath, fatigue

Less Likely: Discomfort from pressure from the echo probe

Rare: For individuals with coronary artery disease, exercise testing is associated with a slight risk of developing serious disturbances in heart rhythm, abnormal increase or fall in blood pressure, fainting, chest discomfort, or very rarely, heart attack (estimate 9 per 10,000 tests or < 0.1%) and death (estimate 2 per 10,000 tests or <0.02%). Stress echocardiographic studies will be performed in the CDL, which is fully equipped with monitoring (blood pressure, 12-lead ECG, pulse oximetry) and emergency equipment (crash cart, intubation, and defibrillation equipment). A physician is immediately available at all times. Optison or Definity injection provides contrast enhancement and may be required for adequate images. Use of Optison or Definity is associated with a less than 1% occurrence of flushing, dizziness, low blood pressure, headache, shortness of breath, or hip or back pain. Allergic reactions (e.g., hives, throat swelling) are rare but possible with Optison or Definity. Allergic reactions can be treated with diphenhydramine or epinephrine.

DXA scan:

Likely: A DXA scan involves exposure to radiation from the X-ray scanner used for the body composition test. The amount of radiation is less than 1 mrem, which is 1% of the amount of radiation exposure all people in St. Louis receive each year from naturally occurring radiation sources. The risk from the radiation exposure in this study is too small to be measured. It is not a big risk when compared with other risks taken every day. Subjects who want to know more about radiation exposure will be referred to the "Radiation Fact sheet" on the Research Participant section of the Human Research Protection Office website at <http://hrpo.wustl.edu> and/or will be given a copy of the fact sheet.

Less Likely: None

Rare: None

¹H-MRS:

Likely: The machine that scans the body during this procedure produces loud noises, which are normal. To protect their hearing, subjects will be required to wear earplugs or earphones during the scan.

Less Likely: None

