Less Likely: Minor side effects include abdominal symptoms (abdominal pain, nausea, vomiting, diarrhea, constipation and flatulence), photosensitivity, myositis or myopathy, and headache. Subjects will be monitored for all of these symptoms and for elevation of liver function tests (alanine aminotransferase [ALT] and aspartate aminotransferase [AST]) as these can become elevated in some patients. Should any of these side effects develop, the subject will be withdrawn from the study.

Rare: There is a minimal risk of allergic reaction (1%). Medication interactions are rare but can occur with oral anticoagulants, HMG-CoA reductase inhibitors, bile acid sequestrants, and cyclosporin. Subjects on anticoagulants or cyclosporine will be excluded. Subjects on bile acid sequestrants and HMG-CoA reductase inhibitors will be monitored closely. Allergic reactions can be treated with diphenhydramine or epinephrine.

24-hour food recall:

Likely: None

Less Likely: None

Rare: Subjects may experience some emotional discomfort or frustration in recalling everything they ate and drank over 24 hours.

Blood glucose and event log:

Likely: None

Less Likely: None

Rare: Subjects may experience some emotional discomfort or frustration from recording their blood glucose levels, distance walked, major illnesses/stresses/side effects, and from reporting this information to the study coordinator each week.

PI: [name]

Placebo:

Likely: None

Less Likely: None

Rare: None

SUBJECT CONFIDENTIALITY

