The Data and Safety Monitoring Plan for this protocol will include adverse event reporting by the PIs on the CARS Data and Safety Monitoring Forms, with oversight and monitoring by the PIs and the Research Subject Advocate (RSA). The PIs and research coordinator will meet weekly to review any study issues, and a Data and Safety Monitoring Board consisting of [name] (Professor of Medicine and Medical Director of the Heart Failure Program at Washington University) and [name], MS (Biostatistician in the Division of Cardiology) will meet every six months with the study coordinator and Study Investigators to review study data, discuss any safety issues, ensure compliance with the protocol, and ensure the subjects' protection against risk.

Serious Adverse Events (SAEs) from this protocol will be reported to the CARS Advisory Committee via the CARS RSA, to the HRPO, and to the NIH. The study will be discontinued if there is clear evidence of harm or

harmful side effects of the procedures. In the event that a SAE occurs that increases the risks to participants, the study will be stopped, an investigation will be conducted, and a findings report generated to the NIH, HRPO, and CARS via the RSA before the study is resumed. Should there be SAEs or AEs that occur at a frequency greater than 5%, they will be added to the consent document, if not already addressed, and enrollment will be halted while a determination is made regarding the potential risks to participants. A report summary will be generated and sent to CARS and the RSA every 6 months. The summary report will include (but is not limited to) who monitored the study, SAEs, AEs, compliance, compliance with data collection, dropouts, and recruitment/enrollment.

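### Does the 5% adverse-event pause on enrolment need a stated denominator, unit, arm and time of assessment?

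*Protocol*

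**What the plan says.** The Data and Safety Monitoring section sets one numeric safety trigger: "Should there be SAEs or AEs that occur at a frequency greater than 5" per cent. The consequence is that "they will be added to the consent document, if not already addressed, and enrollment will be halted while a determination is made" about the risk to participants.

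The same section describes two review cycles and ties the trigger to neither. For the investigators, "The PIs and research coordinator will meet weekly to review any study issues". The Board "will meet every six months with the study coordinator and Study Investigators to review study data". The section also provides for discontinuation on clear evidence of harm, and for stopping and investigating after a serious event that raises the risk to participants.

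Three other places bear on how the trigger would be read:

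- Risks of this Study, Stress Echocardiography: "Likely: Shortness of breath, fatigue". This test belongs to the screening visit.
- Methods, Visit 2: "After this baseline testing is complete, subjects will be randomized", in a blinded fashion. Stress-test events therefore arise before allocation.
- Risks of this Study, Fenofibrate: "There is a minimal risk of allergic reaction (1" per cent), the only rate given for a drug effect. For the minor side effects and raised liver tests listed just before it, "Should any of these side effects develop, the subject will be withdrawn from the study".

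**The concern.** A frequency needs a numerator, a denominator and a moment of counting, and the sentence supplies none of them outright. The denominator could be subjects screened, randomised or treated to date. The numerator could be one type of event or any event, pooled or by arm. The count could be made weekly or every six months. It is also possible to ask whether effects already in the consent form count towards the pause, because the phrase exempting them sits next to the consent update.

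These choices affect how often the rule fires. Early in the trial a threshold of 5% is passed by a single event. If breathlessness during an exercise test were logged as an adverse event and counted, the protocol would pause recruitment for something that it rates as likely. At stake are needless pauses, and disagreement over whether the rule had been followed.

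**Working it through.** The protocol states no operating characteristic for this rule, so there is no figure of its own to reproduce. The check has two parts: what the text already settles, and how often the rule fires on that reading.

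**What the text settles**

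- *Unit.* The events that pass 5% are to be added to the consent document unless already covered there. Only a named event can be added to a consent form; an overall any-event rate cannot. The wording points to event type.
- *Arm.* Allocation is blinded, and the Board meets with the coordinator and investigators. No closed session or unblinded count is described. Pooled counting is what the described procedures allow.
- *Listed effects.* The exemption qualifies the consent addition only. On a plain reading the pause covers listed and unlisted effects alike.
- *Not settled.* The denominator, and the review at which the frequency is assessed.

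**Threshold arithmetic** (strictly greater than 5%)

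- One event: 1/19 = 5.26% passes and 1/20 = 5.00% does not, so one event suffices up to 19 subjects.
- Two events suffice up to 39 subjects (2/39 = 5.13%), and three up to 59 (3/59 = 5.08%).

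The figure of 19 needs a count updated after every subject. At six-monthly reviews the picture differs, as follows.

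**Pace.** The Inclusion/Exclusion section gives a goal of 130 subjects and enrolment from 4/1/12 through 2/28/18, which is 71 months. Even accrual is assumed. 130/71 × 6 = 11.0 subjects per six months, or about 0.42 per week. Reviews then fall at about 11, 22, 33 and so on. One event among subjects 12 to 19 is first seen as 1/22 = 4.5%, which gives no pause.

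**Chance of a pause over 130 subjects.** Inputs: 1% on fenofibrate (the stated rate for allergic reaction), 0% on placebo and 1:1 allocation (both assumed). The pooled rate is 0.5%. The method is an exact binomial recursion, with a pause if the pooled proportion exceeds 5% at any review.

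| Review schedule, pooled | Chance of a pause |
|---|---|
| every 10 subjects | 0.054 |
| every 11 subjects | 0.055 to 0.064 |
| every 12 subjects | 0.065 |
| after every subject | 0.091 to 0.100 |

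The ranges reflect which arm comes first in an alternating sequence. Nearly all of the six-monthly figure comes from the first review: 1 − 0.995^11 = 0.054.

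**Higher assumed rates, pooled, six-monthly, same rate in both arms.** A true 1% gives 0.12 to 0.14, 3% gives 0.44 to 0.48, and 5% gives 0.76 to 0.79. The rule fires more often as the true rate nears the threshold, as a screening trigger should.

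**Cost of a pause.** At 0.42 subjects per week, a pause of four weeks (an assumed length) defers 4 × 0.42 = 1.7, or about two subjects.

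**The case for a change.** The strongest case for a change is that this is the only numeric safety trigger, that the protocol itself fixes it, and that its behaviour depends heavily on what is left out. With a true 1% rate in all subjects, a running count pauses enrolment at some point with probability 0.192. Measuring against a fixed 130 (seven or more events) gives 0.0004. A monitor could not say from the sentence alone which of these applies.

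The arithmetic is right, but the contrast overstates the ambiguity. Dividing events to date by a planned total that includes people not yet enrolled is not an observed frequency, so that extreme is not a natural reading. Other large figures also rest on readings that the text hardly supports. Counting any event, with the nine fenofibrate side-effect terms at an assumed 0.5 to 2% each, gives 0.68 to 1.00. Counting by arm at 1% on fenofibrate gives 0.16 to 0.19.

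The stress-test example keeps some force, because listed effects do appear to count. At an assumed 10 to 30%, 11 exposed subjects would trigger a pause with probability 1 − 0.9^11 = 0.69 to 1 − 0.7^11 = 0.98. But the protocol does not say that expected exertional symptoms are recorded as adverse events. Nor is 11 the number exposed: screen failures also have the test, and some enrolled subjects may skip it because of a recent one. A pause of this kind would end once the symptoms were recognised as expected.

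What stands is that the denominator and the review at which it is applied are unstated.

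**Conclusion.** The gap is real but narrow, and it calls for no change to the plan. Event type, pooled counting and the inclusion of listed effects follow from the wording and the blinded conduct. The remaining choices, the denominator and the time of assessment, are ones that the investigators and Board will make in applying the rule, and the monitoring documents, which are not shown here, may already hold them.

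On the best-supported reading with six-monthly review, the chance of a pause is about 0.05 to 0.06 over the trial; with review after every subject it is 0.09 to 0.10. Both rest on the stated 1% drug rate, an assumed 0% on placebo, 1:1 allocation and even accrual to 130. Higher true rates give more pauses.

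If the rule fires early on a single event, the result is a temporary pause and a judgement about risk, which errs towards caution. The clear-harm clause, the serious-event stop, weekly review and withdrawal for listed drug effects operate whatever reading is taken. Nothing in the section is contradicted or miscalculated, and no treatment estimate or conclusion depends on the choice.
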